### **3.a COVID-19 Specific SilverCloud Module**

During the COVID-19 pandemic, coaches in the SilverCloud intervention will be randomized into either condition:

---

1. Give the COVID-19 modules to their users in addition to their assigned SilverCloud modules to treat depression, anxiety, and/or eating disorders, following the same schedule as for transdiagnostic modules.
2. Only providing their users with their assigned SilverCloud modules to treat depression, anxiety, and/or eating disorders.

## **E Participants will not be aware of this randomization to prevent bias when answering surveys. Study Procedures**

### ***E1 Screening for Eligibility***

Eligibility will be assessed using the measures and cut-offs in the table below.

**Table 3. Screening Measures and Cut-Offs for Anxiety, Depression, and Eating Disorders**

Construct	Measure	Cut-off score	Projected prevalence
Anxiety disorders			
Generalized anxiety disorder, at high risk	GAD-Q-IV	5.7	14%
Generalized anxiety, clinical	GAD-Q-IV	diagnostic criteria	8%
Social anxiety disorder, at high risk	SPDQ	7.4	15%
Social anxiety disorder, clinical	SPDQ	diagnostic criteria	9%
Panic disorder, at high risk	PDSR	8.8	2%
Panic disorder, clinical	PDSR	diagnostic criteria	2%
Depression			
Depression, at high risk	PHQ-9	6-10	15%
Depression, clinical	PHQ-9	11	15%
Eating disorders			
Eating disorder, at high risk	WCS, EDE-Q	WCS of 47, plus non-clinical level of compensatory behaviors	10%
Eating disorder, clinical	EDE-Q	2.3 plus diagnostic criteria	8%
Overall projected prevalence			
At high risk for $\geq 1$ condition (none clinical)	see above	see above	25%
No current treatment			15%
Clinical for $\geq 1$ condition	see above	see above	30%
No current treatment			15%

Notes: GAD-Q-IV=Generalized Anxiety Disorder Questionnaire-IV; SPDQ=Social Phobia Diagnostic Questionnaire; PDSR=Panic Disorder Self-report; PHQ-9=Patient Health Questionnaire; WCS = Weight Concerns Scale; EDE-Q = Eating Disorders Examination-Questionnaire. Data source for projected prevalence numbers: Healthy Minds Study 2014-2016 (N=66,633)

Participants will also be asked if they own a smartphone and if they are currently in treatment for mental health.

### ***E2 Schedule of Measurements***

Participants will be assessed at screening, baseline, 6 weeks, 6 months, and 2 years. All surveys will be administered via Qualtrics. Participants will be compensated by receiving an electronic gift card for completing the Baseline (\$5), 6 week (\$5), 6 month (\$10), and 2-year (\$20) follow-up assessments. Participants will be entered into a sweepstakes to win one of five \$50 gift cards after completing the Baseline, 6 week, 6 month, and 2-year surveys. In addition, once participants complete all four surveys, they will be entered into a sweepstakes to win one of ten \$100 gift cards.

---

All students who receive a recruitment email will be automatically entered into a sweepstakes for one of 40 \$100 electronic gift card prizes.

See table below for schedule of assessments:

	Baseline Screen	Intervention Period	Post-Screen Assessments			Primary Purpose
			6 wks	6 mos	2 yrs	
PARTICIPANTS						
Demographics	x					Mod
Expectancy/credibility	x					Mod
Degree of cognitive distortion	x					Mod
Anxiety: Generalized anxiety; social phobia; panic	x		x	x	x	TO/Mod (symptom severity; comorbidity)
Depression	x		x	x	x	TO/Mod (symptom severity; comorbidity)
Eating disorders	x		x	x	x	TO/Mod (symptom severity; comorbidity)
Chronicity	x					Mod
Comorbidities: Trauma; insomnia; substance use	x			x	x	Mod
Impairment/quality of life	x			x	x	TO/Mod
Motivation for treatment	x		x	x	x	Mod
Mental health treatment utilization	x		x	x	x	TO
Academic impairment (obtained from colleges)	x			x	x	TO
Target engagement Transdiagnostic : dysfunctional cognitions; CBT skills Disorder-specific : avoidance; behavioral activation; restraint; weight/shape concerns	x		x			Med
Early engagement			x			Med
Rapid response			x			Med
Screening and treatment feedback				x	x	--
TREATMENT PROCESS (INTERVENTION CONDITION)						
Mobile treatment process (e.g., sessions completed, messages with coach)		x				Pred
Fidelity/personalization of coaching (i.e., user perception and coder ratings)		x	x	x		Pred
STUDENT MENTAL HEALTH SERVICES CENTERS						
Attitudes toward mobile mental health platform	x					--
Perceptions of mobile mental health platform				x		--
Intended adoption					x	--
Mental health service utilization	x				x	TO

Notes: Light gray shading = occurring during intervention period. Mod = moderator; TO = treatment outcome; Med = mediator; Pred = predictor.

## 2.a Data Collection Procedures for Adverse Events

For the purpose of this study, adverse events will be defined as unanticipated problems involving risks to the study participant. A serious adverse event will be defined as any untoward occurrence that results in death, is life threatening, or creates persistent and

---

significant disability. The initial step in reporting adverse events of any kind is to consult with [name], PI at PSU, who will be providing oversight for adverse event reporting for the study. Additionally, adverse events will be reported to PIs at the other sites, Drs. [name] (WUSM), [name] (UM) and [name] (PAU), who will decide if the event is serious enough to warrant treatment discontinuation or participant withdrawal. Any potentially adverse events will be evaluated by the PIs within 72 hours. All serious adverse events will be immediately reported to the IRB of Record. All adverse events and study withdrawals, together with a detailed explanation of the event and withdrawal, will be forwarded to the Human Subjects Committee and the DSMB. In addition, at its regular meeting, the DSMB will summarize all adverse events of any severity, to be forwarded to the IRB of Record via [name].

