## **2.b Ethical Considerations**

All key personnel involved in the design or conduct of research involving human subjects will receive the required education on the protection of human research participants prior to the start of the study. Participants will be informed that they do not have to answer any questions that make them uncomfortable. There are minimal risks for participants in the mobile health intervention. Coaches in SilverCloud Health will be recruited at the study four participating sites. Coaches will be students in a graduate program in psychology, counseling, or social work. Coaches will be trained and under the close supervision of a coach supervisor, at WUSM and PAU who licensed psychologists, as well as the Fidelity Monitoring Center.

Given national data showing that nearly 10% of students have seriously considered suicide in the past year and that rates of suicide on university campuses continue to increase, suicidality will be consistently monitored throughout the study, including within the mobile intervention itself and through the completion of the baseline and 6-week, 6-month, and 2-year follow-up assessments. Students who endorse any suicidality on these assessments will receive immediate follow-up, including a referral to seek in-person care. Despite the perceived risk that assessing suicidality will increase suicidality, research supports that asking about this does not increase suicidality and, among those who may endorse active suicidal plans or intent, may lead to improvements in health seeking behaviors and increased safety. Notably, we decided not to exclude students with suicidality, given that only 20-40% of college students with mental health problems receive treatment. As such, we deemed it insufficient to exclude such individuals from receiving the intervention and only providing an in-person referral, given the goal of this proposal to narrow the treatment gap.

---

Participant safety is of utmost clinical import, and several safety precautions and procedures will be implemented.

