## **2.b Reporting Procedures**

Because the online interventions follow standard practice guidelines that have been used in research trials without significant adverse events, we do not anticipate any significant adverse events. However, coaches will be trained to monitor for adverse events, including Serious Adverse Events (SAEs) such as deaths, hospitalizations, and life threatening events and Unanticipated Problems (UPs), and will report any potential adverse events immediately upon their identification to the FMC. We will also monitor for adverse events at all follow-up assessments and via all other communication with study participants. Any potentially adverse events will be evaluated by the PIs within 72 hours. Serious adverse events will be promptly reported to the study IRB. Study-related serious adverse events will be reported to the NIMH within 2 weeks; all others will be included in the annual report to the NIMH.

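### Section E2 2.a limits adverse events to unanticipated problems while 2.b does not, so expected non-serious harms may go unrecorded and no comparison of harms by arm is planned

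*Combined protocol and SAP*

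**What the plan says.** The only formal definition is in E2 2.a: "adverse events will be defined as unanticipated problems involving risks to the study participant". The sentence that follows is wider: "A serious adverse event will be defined as any untoward occurrence that results in death, is life threatening", or that leaves lasting and significant disability. It is not restricted to unexpected events, and it does not mention hospitalization.

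E2 2.b asks coaches to watch for adverse events, "including Serious Adverse Events (SAEs) such as deaths, hospitalizations, and life threatening events and Unanticipated Problems (UPs". Here unanticipated problems are one component, and hospitalization appears among the serious events. The section adds: "We will also monitor for adverse events at all follow-up assessments and via all other communication with study participants".

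Under 2.a, adverse events are forwarded to the Human Subjects Committee and the DSMB, and at its regular meeting "the DSMB will summarize all adverse events of any severity".

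Elsewhere the protocol names harms that it expects to meet. D2 2.b (Ethical Considerations) notes that "nearly 10% of students have seriously considered suicide in the past year", has coaches look each week for changes such as more purging, and provides for possible anorexia nervosa at 6 months or 2 years. D2 2.e (Risks and Benefits) accepts that such programs may draw more attention to symptoms. These sections prescribe monitoring, referral and risk procedures. None says that the event is recorded or tabulated as an adverse event.

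**The concern.** The DSMB summary and the annual adverse-event review in H1 take their scope from the definition. The promise to cover every severity does not help if an event is screened out before its severity is graded. Two staff members could classify the same non-serious deterioration in opposite ways, one following 2.a and the other 2.b, and both would be following the protocol.

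What is at stake is the trial's account of harm. A guided self-help program is compared with referral in students selected for symptoms, including students with suicidality. A low adverse-event count could reflect the definition and not what happened to participants. If coaches report what they see, the count could instead be higher in the intervention arm only because that arm is watched more closely.

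**Working it through.** No figure in the plan depends on the definition, so the check is a side-by-side reading of E2 2.a and 2.b against the harms that the protocol names.

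| Event | Where the protocol foresees it | Adverse event under 2.a | Serious under 2.a | Covered under 2.b |
|---|---|---|---|---|
| Death, life-threatening event | D2 2.b (imminent risk) | not needed, see next column | yes | yes |
| Hospitalization that is not life threatening | E2 2.b | only if unanticipated | not listed | yes, as serious |
| Suicidal ideation that is not life threatening | D2 2.b, 2.e | no, if anticipated | no | not settled |
| Increased purging, other worsening | D2 2.b, 2.e | no, if anticipated | no, unless it meets a listed criterion | not settled |
| Possible anorexia nervosa at 6 months or 2 years | D2 2.b | no, if anticipated | no, unless it meets a listed criterion | not settled |

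The first row is safe. The second shows that the two sections disagree on what is serious. The last three show the gap: 2.a leaves the event out and 2.b does not clearly bring it in.

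The next question is whether the analysis plan fills the gap. F3 models uptake, clinical-case status, symptoms and quality of life by arm, then mediators, predictors, moderators, costs, academic outcomes and attitudes. It has no adverse-event table, no proportion of individuals who deteriorate and no comparison of new suicidality. F4 deals only with missing data.

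The case-status outcome is a poor substitute. F1 plans about 3,154 high-risk and 3,154 clinical participants with complete follow-up, so 3,154 / (3,154 + 3,154) = 50% are already clinical at entry. If a positive screen means meeting the clinical criteria, these students can only stay a case or stop being one, so their worsening cannot appear in that outcome. The symptom models do register it, but only within an average, where improvement in others can offset it. The moderator models look for subgroups defined at baseline and do not count individuals who worsen.

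The last question is detection. Both arms share the follow-up surveys and other contact with the study team. Only the intervention arm has coaches, the platform flag on the PHQ-9 suicidality item and weekly symptom monitoring (D2 2.b, D3). A pooled event count would therefore mix a treatment difference with a surveillance difference.

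**The case against.** The strongest reply is that serious harm is covered. The serious-event definition in 2.a has no restriction to unexpected events, and 2.b adds hospitalization and asks coaches to report any potential event. A reader might infer from the opening definition that suicide attempts or psychiatric admissions go uncounted. The documents do not support that: a death or life-threatening attempt is caught under 2.a, and an admission under 2.b.

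It can also be argued that 2.b, in saying "we do not anticipate any significant adverse events", makes any significant deterioration unanticipated and so reportable. That reading is possible. That it must be argued for shows the ambiguity.

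A reader might go further and conclude that the DSMB and later readers would have no means of judging harm. That is too strong. Symptoms are measured in both arms at 6 weeks, 6 months and 2 years, and average change is compared. Suicidality is assessed at baseline and every follow-up. Under H1 the DSMB reviews intervention effects and safety, can request further safety data and selects analyses. An average net harm would be visible. What is missing is a planned view of individual worsening by arm.

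It is also tempting to attach a number by taking 10% of half the planned sample: 7,884 / 2 = 3,942, and 10% of that is 394 per arm. The documents do not support this as a count of missed events. The 10% is past-year national prevalence among students. Because students with suicidality are admitted, it would include ideation already present at entry. No rate is given for this population.

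Finally, a broader definition has a real burden. Under E2, potential adverse events are evaluated by the PIs within 72 hours, and each adverse event is forwarded with a detailed explanation. Sending every expected survey response down that route would be heavy. This objection stands, and the fix has to allow for it.

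**Conclusion.** The point holds for anticipated, non-serious harms. E2 2.a and 2.b give incompatible accounts of what an adverse event is. If the formal definition in 2.a is followed, harms that the protocol itself names can be left out of the adverse-event record and the DSMB summary, and F3 does not recover them by arm. The two sections also disagree on hospitalization, and coach detection makes raw event counts non-comparable between arms.

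This rests on two assumptions: that 2.a governs because it is the only formal definition, and that a harm named in the protocol counts as anticipated. Its size cannot be stated as a number of events. The primary efficacy analysis is unaffected. The weakness lies in harms reporting and should be corrected.

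**What to change.** 1. Reconcile E2 2.a and 2.b. Define an adverse event as any untoward occurrence during participation, anticipated or not. Keep unanticipated problems as a subset with their own reporting rule. Make the two sections agree on whether hospitalization is a criterion for a serious event.
2. Add to F3 a safety table by arm, derived identically in both arms from data already collected: individual symptom deterioration and new suicidality relative to baseline at 6 weeks, 6 months and 2 years, and possible anorexia nervosa at 6 months and 2 years. Fix the definition of deterioration in advance and show the number assessed in each arm at each time.
3. List coach-detected events separately, marked as available in the intervention arm only.
4. State that expected, non-serious events found through surveys go to the DSMB as aggregate tables, so that they do not each enter the 72-hour evaluation and individual-explanation route. Serious events and unanticipated problems stay on that route.

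The cost is revised wording, some extra analysis and more events logged. No survey, visit, participant or treatment procedure is added, and the existing monitoring and referral procedures are untouched.

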## **2.b Reporting Procedures**

Because the online interventions follow standard practice guidelines that have been used in research trials without significant adverse events, we do not anticipate any significant adverse events. However, coaches will be trained to monitor for adverse events, including Serious Adverse Events (SAEs) such as deaths, hospitalizations, and life threatening events and Unanticipated Problems (UPs), and will report any potential adverse events immediately upon their identification to the FMC. We will also monitor for adverse events at all follow-up assessments and via all other communication with study participants. Any potentially adverse events will be evaluated by the PIs within 72 hours. Serious adverse events will be promptly reported to the study IRB. Study-related serious adverse events will be reported to the NIMH within 2 weeks; all others will be included in the annual report to the NIMH.

## **2.c Adverse Event Reporting Period**

## **2.d Post-study Adverse Event**

## ***E3 Study Outcome Measurements and Ascertainment***

Study outcomes includes the following:

- Reducing the number of individuals with mental health disorders.
- Reducing disorder-specific symptoms
- improving quality of life and functioning

## **F Statistical Plan**

### ***F1 Sample Size Determination and Power***

Sample size was based on achieving greater than 80% power to detect minimally meaningful differences in primary and secondary outcomes. We will include 20 colleges with approximately equal numbers of participants per campus, and approximately 3,154 high risk and 3,154 clinical participants with complete follow-up data. All power estimates were derived from Monte Carlo simulations (a gold standard in power estimation). For all analyses, power estimation is based on an effect size of .2 (i.e., for the primary

---

outcome, a differential change of .2 in the treatment vs. control group; for moderator analyses, effect size was .2 for each moderation effect; for mediator analyses, each pathway within the mediation was estimated at .2). We thus have power to detect smaller differences than we anticipate based on assumptions; this extra power is important, given that smaller differences would still be clinically meaningful at a population scale, particularly considering the modest cost of this online intervention. Power for all secondary outcomes was also estimated within the Monte Carlo simulation using all moderators within the same model; and all mediators within the same model targeting a .2 effect size, reflecting a conservative approach to power calculation and model estimation. Results of the Monte Carlo simulations suggested we had greater than 90% power to detect all primary outcomes and greater than 80% power to detect all secondary outcomes.

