## **C Study Objectives**

### ***C1 Study Aims***

Our study aims are as follows:

- 1) Aim 1: Examine uptake (i.e., individuals beginning treatment) of the mobile mental health platform compared to referral to usual care.
- 2) Aim 2: Evaluate the effectiveness of the mobile mental health platform, compared to usual care, in (2a) reducing the number of individuals with mental health disorders (primary outcome); (2b) reducing disorder-specific symptoms (secondary outcome); and (2c) improving quality of life and functioning (secondary outcome).
- 3) Aim 3: (3a) Examine if the mobile intervention changes targets previously found to be associated with outcomes, both transdiagnostic (i.e., decreased dysfunctional cognitions, increased use of CBT skills) and disorder-specific (i.e., reduced avoidance for anxiety, increased behavioral activation for depression, reduced dietary restraint and weight/shape concerns for EDs); (3b) determine if changes in targets are associated with clinical benefit; and (3c; exploratory) identify other putative mediators of change (e.g., early engagement in help services, rapid response), (3d; exploratory) within-mobile program predictors of outcome (e.g., sessions completed), and (3e; exploratory) treatment moderators.
- 4) Aim 4 Evaluate stakeholder-relevant outcomes: (4a) costeffectiveness; (4b) students' academic performance; and (4c) attitudes.

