We also propose several mediators, which fall into: 1) primary intervention targets/mechanisms, considered most essential to outcomes (some of which are transdiagnostic and some disorder-specific; and 2) other mediators—early engagement in services and rapid response. CBT theory posits that the most important ways to change symptoms are by changing cognitions and/or changing behaviors. Thus, our transdiagnostic targets are decreased dysfunctional cognitions and increased use of CBT skills. Empirical support for cognitive changes suggests that they are central to reduction in anxious and depressive symptoms. For EDs, although only a few studies have examined change in cognition, it is worth including given its emphasis in CBT theory. There is evidence that acquisition of CBT skills (e.g., challenging thoughts) is another critical target at least for anxiety and depression. Our disorder-specific, evidence-based targets are as follows: reducing avoidance, associated with changing anxiety; increasing behavioral activation, associated with reducing depressive symptoms; and reducing dietary restraint and weight/shape concerns for reducing EDs. We will examine whether the mHealth platform leads to change in the targets listed above and whether target change is associated with clinical benefit. Use of any potentially helpful services (e.g., Lantern, self-help, face-to-face therapy, medication) is also likely to lead to change, particularly in the first 6 weeks. Thus, while not a specific target of intervention, early engagement in help services is a potential mediator of symptom reduction and will be tested. Rapid response in symptoms, with rapid response usually defined as  $\geq 50\%$  reduction in symptoms occurring within the first 4-6 weeks of treatment, predicts longer-term outcome in anxiety, depression, and EDs and is considered a mediator. Within-mobile program indices will be tested as predictors of outcome, including sessions completed, number of messages sent by user and coach, techniques completed, time spent with the program, and coach personalization (i.e., assessed through users' perception and coding a subset of messages. Finally, data will be used to explore moderators—subgroups for whom further tailoring or more intensive services are needed in future iterations. Moderators exploratory and based on prior work; they are: gender, race/ethnicity, expectancy/credibility, symptom severity, duration of problem, comorbidity, disorder for which the person sought treatment, degree of cognitive distortion, impairment, family income, and motivation.

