## ***F3 Analysis Plan***

To evaluate efficacy of the mHealth platform vs. usual care, in engaging participants (Aim 1) we will use hierarchical logistic regression to examine uptake (i.e., individuals beginning any sort of treatment). Outcome will be at least one session of mental health services use (either online or in-person) assessed at 6 weeks, 6 months, and 2 years. Using hierarchical logistic regression, we will also examine efficacy in reducing or preventing number of students with mental health disorders (i.e., a positive screen for at least one of anxiety, depression, or ED as the outcome reflecting a "clinical case") assessed at 6 weeks, 6 months and 2 years, with a primary endpoint of 2 years. This allows for a single, universal outcome applicable to everyone in the study. Both logistic regression models will include random intercepts for colleges and for students nested within colleges, and account for repeated assessments within students, and will estimate the following fixed effects: main effect of time (coded as a factor variable, including baseline, 6-weeks, 6-months, and 2 years), treatment condition, and two-way interaction between time and treatment condition.

To evaluate reduction in disorder-specific symptoms (Aim 2b) and improvement in quality of life (Aim 2c), multilevel models will be used. Analyses of symptom change will be conducted within each clinical disorder subgroup separately with relevant symptoms as the response variables. We will also use a z-score to standardize primary symptom measures to obtain an estimate for a unified intervention effect. All symptom models will include random intercepts for colleges and for students nested within colleges, account for repeated assessments within students, and will estimate the following fixed effects: main effect of time, treatment condition, and two-way interaction between time and treatment condition. Parameter estimates from these models will allow separately

---

comparing change between arms from pre to 6 weeks, pre to 6 months, and from pre to 2-year follow-up. Each model will use dummy-coded factor terms as a stringent test of the treatment to ensure that: 1) treatment was associated with significantly greater change from pre to post than the control group; and 2) gains made in treatment at 6 weeks are maintained and significantly greater than baseline at each follow-up.

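### Does F1's claim of more than 80% power for all secondary outcomes fail because F3 analyses symptoms disorder by disorder?

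*Combined protocol and SAP*

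**What the plan says.** F1 (Sample Size Determination and Power) sizes the trial at about 3,154 high-risk and 3,154 clinical students with complete follow-up. It targets an effect of .2 throughout; on moderators it says "for moderator analyses, effect size was .2 for each moderation effect". It adds: "Power for all secondary outcomes was also estimated within the Monte Carlo simulation using all moderators within the same model". The stated result is "greater than 90% power to detect all primary outcomes and greater than 80% power to detect all secondary outcomes". F1 gives no alpha, no SD scale for the .2, no moderator coding and no sample size by disorder.

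C1 makes disorder-specific symptoms (Aim 2b) and quality of life (Aim 2c) secondary outcomes, and labels treatment moderators (Aim 3e) exploratory. C2 repeats that label: "Moderators exploratory and based on prior work; they are: gender, race/ethnicity, expectancy/credibility", followed by others that include the disorder for which the person sought treatment.

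F3 (Analysis Plan) says of Aim 2b: "Analyses of symptom change will be conducted within each clinical disorder subgroup separately with relevant symptoms as the response variables". It then adds a pooled analysis: "We will also use a z-score to standardize primary symptom measures to obtain an estimate for a unified intervention effect". The fixed effects listed for these symptom models are time, condition and their interaction. Moderators come later, in the Aim 3 paragraph, as three-way interactions with time and condition. That paragraph does not name the outcome or say whether the models are pooled or split by disorder.

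**The concern.** Read together, these statements seem to promise that moderators of disorder-specific symptoms are tested inside each disorder subgroup with more than 80% power. An interaction with a two-group moderator needs four times the sample of a plain treatment effect of the same size, and the disorder subgroups are only part of the clinical sample. If the promise were meant that way, it would fail.

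Two things would be at stake. A reader might treat a null moderator result for eating disorder, depression or anxiety symptoms as informative when the test had little chance of finding a .2 effect. And F3 uses significant moderators to choose which mediator analyses are repeated by subgroup, so missed moderators would carry forward. The primary outcome ("a positive screen for at least one of anxiety, depression, or ED") uses everyone and is not touched.

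**Working it through.** **Inputs from the documents.** Completers: 3,154 clinical, 6,308 in all (F1). Effect: .2 (F1). Clinical prevalence (Table 3): eating disorder 8%, depression 15%, generalised anxiety 8%, social anxiety 9%, panic 2%, any clinical condition 30%.

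**Assumptions, because F1 is silent.** Two-sided 0.05, 1:1 allocation, .2 in SDs of change, a 50/50 two-group moderator, and subgroups limited to clinical cases in proportion to Table 3.

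**Subgroup sizes.**
- Eating disorders: 3,154 × 8/30 = 841.
- Depression: 3,154 × 15/30 = 1,577.
- Anxiety: 3,154 × 9/30 = 946 if the three anxiety disorders overlap fully, up to 3,154 × 19/30 = 1,998 if they do not overlap.

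**Can F1's figure be reproduced?** For a plain treatment effect, SE = 2/√n, power = Φ(0.2√n/2 − 1.96), and 80% power needs 4 × (2.80/0.2)² ≈ 785. For a two-group moderator, SE = 4/√n, power = Φ(0.2√n/4 − 1.96), and 80% power needs 16 × (2.80/0.2)² ≈ 3,140 (2.80 is 1.960 + 0.842, rounded).

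| Population | n | Treatment effect of .2 | Two-group moderator of .2 |
|---|---|---|---|
| Eating disorders | 841 | 82.6% | 31% |
| Anxiety, full overlap | 946 | 86.8% | 34% |
| Depression | 1,577 | 97.8% | 51% |
| Anxiety, no overlap | 1,998 | 99.4% | 61% |
| All clinical | 3,154 | >99% | 80% |
| All completers | 6,308 | >99% | 98% |

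A simple simulation (4,000 runs per size) gave 32%, 49%, 60%, 80% and 98% for the moderator at 841, 1,577, 1,998, 3,154 and 6,308. So F1's claim is met for the treatment effect in every subgroup and for an even two-group moderator in a pooled model. It is missed only when that moderator is tested within a disorder.

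**Which model does the plan describe?** The phrase about separate disorder subgroups stands in the Aim 2b paragraph, whose models contain no moderators. The moderator paragraph contains no such phrase. Since the disorder for which help was sought is itself a listed moderator, at least one model has to span disorders; inside a single-disorder subgroup that variable has little left to explain.

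**How far does the shortfall depend on unstated choices?**
- *Continuous moderator, .2 per SD, tested alone:* 785 completers suffice. Power is 83% for eating disorders, 98% for depression and 87% to 99% for anxiety.
- *.2 as a standardised coefficient of the interaction term:* with centred coding, power at 841 is Φ(0.2√841 − 1.96) = Φ(3.84), over 99%. With 0/1 coding the product has SD √(3/16) = 0.433, so the contrast is 0.2/0.433 = 0.46 and power is Φ(0.46 × 29/4 − 1.96), about 92%.
- *High-risk students included* (6,308 × share of 55%): eating disorders 2,064 (62%), depression 3,441 (83%), anxiety 2,753 to 5,735 (75% to 97%).
- *30/70 moderator, .2 in SDs of change:* 26% for eating disorders, 44% for depression, 73% at 3,154 and 95% at 6,308.

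**The case for a change.** The best case for acting is that F1 makes no exception. It says all secondary outcomes, it says the moderators were in the model, and disorder-specific symptoms are a secondary outcome. Gender and race/ethnicity, which are categorical, head the moderator list, so the continuous-moderator result does not rescue the sentence for them. For eating disorders the shortfall survives most variations: 62% with high-risk students added, and on a raw-SD scale 80% would need a baseline to 2-year correlation of about .87. F3 also keeps unstandardised disorder-specific symptom scores as outcomes in its mediator analyses, so pooling cannot be presumed everywhere. Naming the simulated sample size and scale would cost a sentence.

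Much of this stands as a description. F1 is loosely worded, and anyone who tests a two-group moderator within the clinical eating disorder group should not expect 80% power at .2 SD of change. The pooled margin in clinical students alone is also thin, since an uneven split takes it below 80%.

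What does not stand is the step from loose wording to error. It would require that F1's sentence fails whether moderators are pooled or split, and it does not: with treatment effects by disorder and moderators pooled, each half of the sentence can be met. The wider reading joins the population of one F3 paragraph to the model of another.

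**Conclusion.** The concern does not hold as an error. F1's figure of more than 80% is reproduced on the most natural reading of F3: at least 82.6% for the treatment effect on symptoms in each disorder subgroup, and 80% to 98% for a 50/50 moderator in pooled clinical or full samples. The low values (31%, 51%, 34% to 61%) are correct arithmetic for an analysis the plan does not specify. They also depend on reading .2 as SDs of change, on a two-group moderator and on clinical-only subgroups; under a standardised coefficient even 841 completers give more than 90%.

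What remains is a gap in reporting: the sample size, scale, alpha and moderator coding behind the simulation, and whether symptom moderators are pooled. Filling it would alter no model, estimate or conclusion. The moderator aim is already called exploratory in C1 and C2, and an analyst who reports moderators by disorder would show interval estimates and say that such tests are imprecise. The assumptions here are two-sided 0.05, 1:1 allocation and subgroup shares taken from Table 3's all-student prevalences.
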